We have previously studied the immunogenicity of the AR, showing that patients with prostate cancer have an increased frequency of AR-specific antibody responses (irrespective of patients' disease stage), and that patients with these antibody responses have a higher level of AR-specific cellular immune responses [53]. Furthermore, we were able to routinely culture peptide-specific cytotoxic T cells from prostate cancer patients (all fifteen patients screened had peptide-specific T cells to at least one of the AR peptides identified [54]). This work also identified two HLA-A2 epitopes (AR805 and AR811) that are naturally presented on the surface of prostate tumor cells, and found that T cells specific for these epitopes had multi-functional cytokine expression and could lyse prostate tumor cells [54]. Taken together, these data show that the AR is also an immunogenic antigen, and thus may be a logical vaccine target antigen.

We have previously evaluated the ligand-binding domain of the AR (AR LBD) as a vaccine target in murine models. We have reported that a DNA vaccine encoding the AR LBD was able to elicit AR-specific CD8+ T cells in immune competent, male mice [55]. Moreover, immunization of prostate tumor-bearing transgenic mice led to an increase in their survival [55]. These findings, and the safety of this approach was confirmed in an IND-enabling study [56]. Given these

findings, a multi-institution phase I clinical trial evaluating the safety and immunological efficacy of this vaccine (pTVG-AR) is nearly complete, having been evaluated in patients with newly metastatic prostate cancer (NCT02411786). To date there have been no serious adverse events related to treatment in 40 patients treated. Preliminarily, that study has demonstrated that immune response to the AR target can be elicited, and that response to AR is associated with a longer time to progression. Given this, and that the pTVG-AR uses the same vector backbone as the pTVG-HP vaccine, the current trial will evaluate these vaccines together, versus pTVG-HP alone, in combination with pembrolizumab.

C. PD-1 blockade and cancer treatment

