Patients who, in the discretion of the treating physician, appear to be benefiting (e.g. declining serum PSA and/or improvement in symptoms despite new radiographic lesions), may continue in protocol treatment after discussion with the sponsor PI. Some subjects may receive NaF PET/CT scans as a standard alternative to bone scintigraphy, in which case these will be used to determine response/progression. Patients will continue to have blood drawn for immune studies, as per study calendar, up to one year after screening, even if off study prior to that time. In particular, evaluations performed at 6-month time point should be performed even if off-study prior to that time, if feasible. At the end of 6 months, patients without progression will continue to receive pembrolizumab every 3 weeks, up to 2 years (32 cycles) maximum, or until radiographic disease progression. Patients on pembrolizumab alone who have PSA rise (25% increase over month 6 value, and minimum of 2 ng/mL rise) will resume a 3-month (4-cycle) follow-on course of vaccine treatment. The goal here is to minimize treatment but maintain a prolonged time to radiographic progression. All subjects who have not come off study earlier for reasons of adverse events, physician/patient discretion or radiographic progression will come off study at the end of two years of total treatment.

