Following these 4 vaccine booster cycles, patients resume pembrolizumab alone cycles to complete 32 total cycles. If criteria are met for additional vaccine booster cycles, these can occur prior to study cycle 29.

- i. END OF TREATMENT (EOT) VISIT (21 +/- 3 days after cycle 32 day 1)
- 1. Physical examination, including vital signs, symptoms and medications assessment, and ECOG performance score.

- 2. Blood draw for CBC, chemistry panel, serum PSA and PAP (can be performed up to 3 days prior to this visit)
- 3. 10 ml peripheral blood (red-top tubes) for sera to evaluate antibody responses, and 100 ml peripheral blood (green-top heparinized tubes) for T-cell response evaluation (can be performed +/- 7 days of this visit)
- 4. CT scan of abdomen and pelvis (CT of chest as clinically indicated), bone scintigraphy (can be performed +/- 7 days of this visit)
 - j. 28-Day Follow Up Visit (28 +/- 7 days after Off-treatment date, if prior to cycle 32)

Off treatment date is defined as the date the decision was made to take the subject off study treatment.

Patients will come off study at the time of disease progression, undue toxicity, or at the discretion of the patient and/or treating physician that it is not in the interest of the patient to continue treatment. A separate follow-up visit is not required for patients completing the EOT evaluation after cycle 32, however for patients coming off study prior to cycle 32, 28-day follow up visit will include the following:

- 1. Physical examination, including vital signs, symptoms and medication assessment, and ECOG performance score.
- 2. Blood draw for CBC, chemistry panel, serum PSA and PAP
- 3. IF NOT ALREADY COLLECTED WITHIN PREVIOUS 60 DAYS: 10 ml peripheral blood (red-top tubes) for sera to evaluate antibody responses, and 100 ml peripheral blood (green-top heparinized tubes) for T-cell response evaluation
 - k. Long-term Follow-Up
- 1. Subjects will be followed for a total of 5 years. Subjects will be contacted by telephone (if not already being seen in clinic) annually for 2 years following the last study treatment to collect clinical information to identify any potential long-term risks. This information has been requested by FDA for all gene delivery trials to assess potential long-term risks. Subjects will be followed for an additional three years (annually for years 3-5) to collect survival status. The specific information to be collected for years 1-2 annually will include:
 - □ Date of contact

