10. RESPONSE MONITORING

m. Safety

All subjects will be assessed at regular intervals, as per the study calendar, for evidence of adverse events by exam, symptoms, and clinical laboratory findings. For these assessments, we will use version 4.0 of the NCI common terminology criteria (CTCAE).

n. Immunological Monitoring

Blood will be collected by peripheral blood draw (up to 210 mL) pre-immunization, and at weeks 6, 12, 24, 36, 48, and 96, for immunological monitoring. From the heparinized blood, peripheral blood mononuclear cells (PBMC) will be prepared by density centrifugation over Ficoll-Paque using standard techniques. PBMC will be used directly for analysis, and residual material cryopreserved in liquid nitrogen using 90% autologous serum collected at the time of blood draw,

Page 49 of 82

or 90% fetal calf serum, and 10% DMSO. Sera will be prepared from the red-top tubes and stored in aliquots at -80°C for antibody analyses. IFNy and granzyme B ELISPOT analysis will be the primary method of analysis and antigen-specific T-cell proliferation, flow cytometric assays of antigen-specific cytokine secretion, and ELISA tests for antigen-specific antibodies, may be included as other methods of analysis. Some of the samples will be batch shipped to [name] laboratory for additional immune analysis as it relates to the gut microbiome. The primary antigens tested will be PAP (experimental), AR LBD (experimental), PSA (negative control), thyroglobulin (negative control) and tetanus toxoid (positive control). The primary immune analysis will be conducted at the 6-month time point, and compared with the pre-treatment time point, and for patients to be evaluable for immune response (primary endpoint), blood (PBMC and serum) from this time point must be available for analysis. However, immune monitoring will be conducted at the other time points indicated in secondary analyses to evaluate kinetic measures of immunity, and evaluate whether durable immune responses of particular phenotypes are elicited and/or maintained. Assays may be conducted at the time of sample collection (fresh) and/or batched and performed at one time from multiple cryopreserved samples collected at different time points. Other methods of effector and regulatory T-cell response to PAP and other human tissue antigens may be used.

i. Quantitative assessment of antigen-specific CD8+ T-cell effector immunity

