8-well replicate assays [36]. Comparison of experimental wells with control, no antigen, wells will be performed using a two-sample t-test, with p < 0.05 (two-sided) defined as a significant antigen-specific T-cell response. A significant antigen-specific response resulting from immunization will then be defined as a PAP-specific and/or AR-specific response detectable at the 6-month post-treatment time point (or other post-treatment time point evaluated) that is significantly higher than to media only (as above), at least 3-fold higher than the mean baseline value, and with a frequency > 10 per 10^6 PBMC.

ii. Assessment of antigen-specific memory T-cell immunity

Ability of T-cell lines to proliferate in response to antigenic stimulation: T-cell proliferation in response to antigen stimulation as a measure of memory T-cell responses may be assessed by a PKH26 dye dilution assay as previously reported [36]. Specifically, PBMC will be labeled in vitro with PKH26 dye (Sigma, St. Louis, MO) according to the manufacturer's recommendation. Tcell cultures with and without antigens will be established in replicates using 2x10⁵ peripheral blood mononuclear cells (PBMC)/well, plated in 96-well round bottom microtiter plates (Corning, Cambridge, MA), in media consisting of RPMI 1640 (Gibco) and supplemented with L-glutamine, penicillin/streptomycin, \(\beta\)-mercaptoethanol and 10% human AB serum (ICN Flow, Costa Mesa, CA). Antigens may include 2 µg/ml of pools of peptides spanning the amino acid sequence of PAP, PSA, and AR LBD, 250 ng/ml tetanus toxoid, and 2.5 µg/ml phytohemaglutinin (PHA). After 6-7 days of culture at 37°C/5% CO₂, cell surface markers will be stained to characterize the T-cell phenotype and memory phenotype of proliferating cells (CD45RO, CCR7). Flow cytometery will be used to identify and enumerate CD3+CD4+ and CD3+CD8+ T cells co-staining for PKH26. The frequency of antigen-specific CD3+CD4+ and CD3+CD8+ T cells will be determined by determining the precursor frequency of PKH26+ events among CD4+ or CD8+ events (estimated from the number of cells and number of cell divisions by dye dilution using ModFit software, Verity Software House, Topsham, ME), and subtracting the mean precursor frequency of proliferating cells under media-only conditions. Other cell surface markers may be assessed, other antigens evaluated, and/or other methods of antigen-specific T-cell proliferation.

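### The primary immune analysis requires a month-6 blood sample, and Section 6 says draws continue off study, but the calendars and Section 9 schedule no month-6 draw for patients who have already stopped treatment.

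*Combined protocol and SAP*

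**What the plan says.** Section 10.n (Immunological Monitoring) lists draws "pre-immunization, and at weeks 6, 12, 24, 36, 48, and 96, for immunological monitoring". It fixes the main comparison: "The primary immune analysis will be conducted at the 6-month time point, and compared with the pre-treatment time point". It then sets the condition for entering that comparison: "for patients to be evaluable for immune response (primary endpoint), blood (PBMC and serum) from this time point must be available for analysis". Other times are kept for supporting work: "immune monitoring will be conducted at the other time points indicated in secondary analyses to evaluate kinetic measures of immunity". The ELISPOT definition of a response accepts a "response detectable at the 6-month post-treatment time point (or other post-treatment time point evaluated"), and the other assay definitions carry the same alternative.

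Section 6 (Endpoints) covers patients who have stopped: "Patients will continue to have blood drawn for immune studies, as per study calendar, up to one year after screening, even if off study". It adds that month-6 evaluations in particular should still be done off study, if feasible.

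The calendars for both arms limit immune blood in cycles 1 to 8 to cycle 3 day 1 and cycle 5 day 1. The month-6 draw is listed under the Cycle 9 pembrolizumab visit (Section 9.e). For a patient who stops before cycle 32, Section 9.j gives one further draw, at the 28-day visit, under a condition: "IF NOT ALREADY COLLECTED WITHIN PREVIOUS 60 DAYS: 10 ml peripheral blood". Section 9.k is then annual contact, by telephone unless the patient is already seen in clinic, with no blood listed.

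In Section 11, F.5.3 describes the Th1 frequencies and the logit model of Th1 response against PSA response. It names no time point and no rule for a missing month-6 sample. The Analysis Populations text makes all randomized patients the primary population for secondary and correlative outcomes. Immune blood is drawn at the lead site only.

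**The concern.** Section 6 relies on a calendar that does not contain the draw it promises. Staff working from the calendar and Section 9 would not take the sample that Section 10.n requires. The patients left out would be those who stopped early, whether for symptoms, toxicity or choice, or after progression.

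Secondary objective 6 asks whether Th1 immunity is associated with PSA response. Time on treatment may well relate to both. The background section reports from the pTVG-AR phase I trial that "response to AR is associated with a longer time to progression", and that PSA declines in the pilot trial were seen mostly in patients with Th1 immunity to PAP. An analysis conditional on staying until month 6 could therefore differ from one in all sampled patients. The two arms could also be selected differently if their progression rates differ as the design assumes.

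**Working it through.** **1. Reproduce the draw schedule.** Week of cycle c day 1 = (c − 1) × 3. Cycle 3 gives week 6, cycle 5 week 12, cycle 9 week 24, cycle 13 week 36 and cycle 17 week 48. End of treatment is 31 × 3 + 3 = week 96. All match Section 10.n, so the month-6 draw is the Cycle 9 visit. Section 9.e allows ± 7 days for it, that is weeks 23 to 25.

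**2. When does the 28-day visit yield blood?** Let s be the week of the off-treatment date. The visit is at s + 4. Blood is due if the last draw was more than 60 days (60/7 = 8.6 weeks) before. With the last draw at week 12:

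s + 4 − 12 > 8.6, so s > 16.6.

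The visit window of ± 7 days moves this threshold between 12 + 8.6 − 5 = 15.6 and 12 + 8.6 − 3 = 17.6.

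| Stop (week) | 28-day visit (week) | Draw due? | Last sample (week) |
|---|---|---|---|
| before 12 | before 16 | depends on last draw | before 16 |
| 12 to 16.6 | 16 to 20.6 | no | 12 |
| 16.6 to 19 | 20.6 to 23 | yes | 20.6 to 23 |
| 19 to 21 | 23 to 25 | yes | 23 to 25, inside the window |
| 21 to 24 | 25 to 28 | yes | 25 to 28 |

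Patients who stop before about week 16.6 have nothing near month 6. For the third and fifth rows a sample exists, but the plan does not say whether it counts as the month-6 sample.

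**3. Which stops fall in the gap?** The 3-month scan does not by itself require stopping (Sections 6 and 7), and Section 9 asks for confirmed radiographic progression.
- Bone progression at week 12 is confirmed at least 6 weeks later, at week 18. The 28-day visit is then at week 22, which is (22 − 12) × 7 = 70 days after the last draw, so blood is due.
- Under iRECIST, confirmation comes at 4 to 8 weeks. At 4 weeks the stop is at week 16 and the visit at week 20, which is 56 days after the last draw, so blood is waived. At 8 weeks the visit is at week 24, 84 days after, and blood is due.
- Stops before about week 16.6 for symptoms, toxicity or discretion fall in the gap.

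**4. How many patients?** The plan gives no rate of stopping treatment. At one end, sites follow Section 6 and no sample is lost. For an extreme scenario, take 30 per arm and the planned 6-month PFS rates. By month 6, 30 × (1 − 0.30) to 30 × (1 − 0.20) = 21 to 24 patients in Arm 1 and 30 × (1 − 0.55) = 13.5 in Arm 2 would have progressed or died. If none of them had the sample, 6 to 9 and about 16 to 17 would remain. This is not a forecast. PFS is not a missing-sample rate, and the second scheduled scan coincides with the Cycle 9 draw. Real counts are also smaller because only the lead site samples, and its share is not stated.

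**The case against.** Section 6 states the intention plainly, and its reference to the calendar can be read as fixing the time points rather than the visits. A careful lead site would take the draw. This stands as to intent, but no visit carries the draw out, and Section 9.j contains a waiver that works against it. Section 8 keeps patients on study after a toxicity stop, with data collected as per protocol, which leads back to the same schedule.

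Nor is an early stopper impossible to score, since the response definitions accept other post-treatment samples and weeks 6 and 12 are collected. That stands. The problem is confined to the primary month-6 analysis and to F.5.3 in so far as it uses it.

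The usual route to a progression stop runs through confirmation, so many such patients would be sampled at the 28-day visit. That largely stands too and narrows the gap to earlier stops.

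Finally, Section 11 defers analysis detail to a later SAP. That can settle denominators and sensitivity analyses, but it cannot recover blood that was not drawn.

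**Conclusion.** The passages conflict and should be reconciled. If the calendar is followed, lead-site patients who stop before about week 16.6 have no sample near month 6, and the primary immune analysis risks selecting patients who stayed on treatment. The week figure rests on nominal visit dates and a last draw at week 12.

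Three stronger readings are tempting but not supported.
- A reader might infer that immune response can be scored only at month 6. The response definitions say otherwise.
- A reader might infer a bias against Arm 2. Suppose exponential progression at 25% and 55% 6-month PFS, so that 1 − √0.25 = 50% and 1 − √0.55 = 25.8% progress by week 12. Suppose also that all of them stop without a later sample, that the true Th1 rate is 40% in both arms, and that responders have half the drop-out risk. Drop-out among responders is then 0.5 × 0.50/0.8 = 31.25% and 0.5 × 0.258/0.8 = 16.1%. The observed Th1 rates are 0.4 × 0.6875/0.50 = 55% and 0.4 × 0.839/0.742 = 45%. The Th1 rate, the halved risk and the stopping rule are not in the documents. The reported link with time to progression concerns AR response, and Arm 1 receives no AR vaccine, so the direction could differ. F.5.3 also names no test of Th1 rates between arms.
- A reader might take the words in brackets in Section 10.n to make immune response a primary endpoint of the trial. The preceding clause concerns the primary immune analysis, and Section 6 names 6-month PFS as the trial's primary endpoint.

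The size and direction of any bias therefore remain open.

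**What to change.** Reconcile Section 6 with both calendars and Section 9. Add a week-24 immune draw, dated from cycle 1 day 1 with the Cycle 9 window, for lead-site patients already off treatment, where feasible. State that the 60-day rule does not waive it.

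In F.5.3, report the number of patients per arm without a month-6 sample. Repeat the Th1 frequencies and the Th1–PSA model on the cycle 5 day 1 (week 12) sample, which is already scheduled.

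Do not count missing samples as non-response in the primary immune analysis. Under the illustrative assumptions in the verdict, that would give 0.4 × 0.6875 = 27.5% in Arm 1 and 0.4 × 0.839 = about 34% in Arm 2, against a true 40% in both. It would exchange one possible distortion for another.

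The cost is one blood draw per early stopper, which Section 6 already calls for, one additional analysis, and wording changes to the calendars, Section 9 and F.5.3.

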2. BACKGROUND AND RATIONALE

A. PAP is a tumor antigen in prostate cancer and PAP-specific CD8+ CTL can lyse prostate cancer cells

PAP was first identified in 1938 and was initially used as a serum marker for the detection of prostate cancer [24, 25]. PAP expression in normal and malignant prostate cells is welldocumented, and is still used in immunohistochemical staining to establish a prostate origin of metastatic carcinoma [26]. The ubiquitous expression of PAP in prostate tissue makes it an appealing antigen as a potential "universal" target for immune-directed therapies of prostate cancer, unlike specific oncogenes that may or may not be expressed by a particular tumor. Moreover, it has been demonstrated that some patients with prostate cancer have preexisting antibody and T-cell responses to PAP, suggesting that tolerance to this "self" protein can be circumvented in vivo [27, 28]. It is also one of only a few known prostate-specific proteins for which there is a rodent homologue, thereby providing an animal model for evaluating vaccine strategies and assessing toxicity [29]. Data from independent labs has demonstrated that, in a rat model, vaccine strategies targeting PAP can result in PAP-specific CD8+ T-cells, the presumed population mediating tumor cell destruction, and anti-tumor responses [30, 31, 32, 33]. PAP is the target antigen of the autologous antigen-presenting cell sipuleucel-T vaccine in which autologous peripheral blood mononuclear cells are loaded ex vivo with a PAP-GM-CSF fusion protein. A separate phase I clinical trial evaluated dendritic cells loaded with a murine homologue of PAP, and demonstrated immunogenicity of this approach [34]. In rodent studies, we have similarly demonstrated that PAP can be immunologically targeted using genetic vaccines, and a plasmid DNA vaccine in particular [31, 32]. We have previously reported the results of two early phase trials conducted in patients with early, PSA-recurrent (non-metastatic) prostate cancer using this same DNA vaccine (pTVG-HP) evaluating the dose and schedule of vaccination [35, 36]. In 38 patients treated, no significant adverse events were observed. Moreover, several patients developed evidence of PAP-specific CD4+ and CD8+ T-cells, and several patients experienced a prolongation in the PSA doubling time, demonstrating immunological efficacy and suggesting a possible anti-tumor effect [35, 36]. The presence of long-term IFNy-secreting immune responses to PAP, detectable at multiple times months after immunization, were associated with increases in PSA doubling time, suggesting this might serve as a rational biomarker for efficacy [37]. Moreover, it was found that immune responses could be augmented months later with repeated

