REPORTING AND RESPONSE DEFINITION: Data will be reported as a mean and standard deviation of antigen-specific (PAP-specific and/or AR LBD-specific) CD4+ or CD8+ T cells expressing one or more cytokines per 10^6 PBMC using triplicate assessments for each antigen-stimulation condition, as previously reported [36]. Comparison of experimental wells with control, no antigen, wells will be performed using a two-tailed Student's t test, with p < 0.05 defined as a significant antigen-specific T-cell response. A significant antigen-specific response resulting from immunization will then be defined as a antigen-specific response detectable at the 6-month post-treatment time point (or other post-treatment time point evaluated) that is significantly higher than to media only (as above), at least 3-fold higher than the mean baseline value, and with a frequency > 100 per 10^6 CD4+ or CD8+ T cells.

iv. Assessment of antigen-specific antibody immunity

Enzyme-linked immunosorbent assay (ELISA) for the detection of antibodies responses to PAP or AR LBD: The presence of a coexisting humoral immune response to PAP, AR LBD, or other antigens will be evaluated by ELISA using an indirect method similar to that described previously [27]. Specifically, Immulon-4 ELISA plates (Dynex Technologies Inc.) will be coated with 2 μg/ml purified PAP or AR LBD protein (Research Diagnostics, Inc., or other antigens or commercial sources) in 0.1 M NaHCO₃/Na₂CO₃ buffer (pH 9.6) overnight at 4°C. After blocking with PBS/1% BSA for 1 hour at room temperature, wells will be washed with PBS + 0.05% Tween-20 (PBS-Tween) and then incubated for 1 hour with human sera diluted 1:25, 1:50, 1:100 and 1:200. After washing, plates will then be sequentially incubated with a peroxidase-conjugated anti-human IgG detection antibody (Amersham), followed by peroxidase enzyme TMB substrate (Kierkegaard and Perry Laboratories). The color reaction will be stopped with 1N H₂SO₄ and the optical density measured at 450 nm. Antibody titers for PAP-specific IgG antibodies will be determined as previously described [27]. Other methods, including Luminex bead-based assays, may substitute for these ELISA methods.

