REPORTING AND RESPONSE DEFINITION: These are not strictly quantitative assays. IgG response will be reported graphically demonstrating sera dilution curves, and by titer – defined as the highest sera dilution at which IgG responses are detectable above the mean + 3 standard deviations of the negative control. A positive IgG response resulting from immunization will be defined as an antigen-specific IgG titer at least 4-fold higher than the baseline titer detectable at the 6-month post-treatment time point (or other post-treatment time point evaluated).

v. Assessment of antigen-spread to other prostate-associated antigens

High-throughput immunoblot (HTI): An exploratory objective of the study will be to determine if patients treated develop "off-target" prostate cancer antigen-specific immune responses as evidence of antigen spread. Future studies may evaluate T-cell responses to non-targeted antigens. However, the primary evaluation will be to evaluate IgG responses to a panel of prostate-associated antigens as we have previously reported in patients treated with vaccines or other immune-modulating agents [88, 89, 90]. IgG specific for 126 antigens, including 29 cancer-testis antigens [91, 92] and 97 prostate antigens frequently immunologically recognized [93, 94, 95, 96] will be identified by screening a high-density phage array expressing these individual antigens, as we have previously reported [88, 90, 91]. An alternative to this approach may include the evaluation of responses to panels of protein antigens fixed to support membranes provided by commercial vendors. The primary analysis will be conducted using sera obtained at 6 months, and compared with IgG responses identified at baseline, to determine whether IgG specific for individual antigens are elicited over time. Other time points will be assessed to determine the durability and kinetics of immune response development, and confirmatory ELISA studies will be performed where feasible.

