Generalized linear models with a logit link function will be used to evaluate PAP-specific and ARspecific antibody responses following treatment with pembrolizumab and DNA vaccine(s), and to determine whether treatment with either sequence elicits immunologic antigen spread to other prostate associated antigens. Logistic regression analysis will be utilized to determine whether pre-existing antigen-specific immunity is predictive of immunological or objective clinical response. The interaction term between pre-existing antigen-specific immunity status and treatment arm will be included in this model and evaluated. Analogously, a generalized linear model with subject specific random effects will be used to determine whether early changes in bone observed by NaF PET/CT are associated with immunological or objective clinical response, or pathological changes associated with immune-cell infiltration. The number and frequencies of second PSA responses in patients treated in follow-on courses will be summarized in tabular format. The stratified (by randomization strata) Mantel-Haenszel test will be used to compare second PSA response rates between study arms. Bacterial, viral and archeal species loads identified from the bioinformatics analysis of the microbiome samples will be compared between pre- vs. post-treatment assessment using a paired t-test. The false discovery rate will be controlled using the Benjamini-Hochberg False Discovery Rate (FDR) method. Logistic analyses will be conducted to determine whether changes in gut microbiota are associated with clinical response.

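### On the ELISA dilution series as written, a patient with a baseline titre of 1:100 or 1:200 cannot be scored as an antibody responder, and a 4-fold rise is undefined below 1:25

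*Combined protocol and SAP*

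**What the plan says.** Section 10.n.iv (antibody immunity) describes an indirect ELISA for PAP and AR LBD in which plates are "incubated for 1 hour with human sera diluted 1:25, 1:50, 1:100 and 1:200". Its reporting paragraph defines titre as "defined as the highest sera dilution at which IgG responses are detectable above the mean + 3 standard deviations of the negative control", and a response as "an antigen-specific IgG titer at least 4-fold higher than the baseline titer", judged at 6 months or another post-treatment time. The same paragraph warns that the assay is only semi-quantitative and asks for dilution curves. The methods text refers to a cited publication for PAP titres, and adds: "Other methods, including Luminex bead-based assays, may substitute for these ELISA methods".

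No rule covers a serum still positive at 1:200, or the value to give a baseline that is negative at 1:25.

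Section 11.w.vi models the PAP and AR antibody responses (exploratory objective 1). For exploratory objective 3 it says: "Logistic regression analysis will be utilized to determine whether pre-existing antigen-specific immunity is predictive of immunological or objective clinical response". It does not say whether immunity there means IgG or T cells. On who may be seropositive at entry, Section 2.A notes that "some patients with prostate cancer have preexisting antibody and T-cell responses to PAP", and Section 2.B reports that AR-specific antibody is more frequent in patients with prostate cancer.

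**The concern.** The response rule asks for a rise that the assay cannot display in part of its own range. A patient whose serum is already positive at 1:100 before treatment has room for one further 2-fold step; a patient at 1:200 has none. Either could have a large true rise and would still be counted as a non-responder.

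Two exploratory analyses are exposed. In objective 1, true responders with a high baseline drop out of the numerator but stay in the denominator. In objective 3, if both predictor and outcome are IgG, the loss falls only on patients with pre-existing antibody. The model could then report that pre-existing immunity predicts failure to respond when it has only detected the end of the dilution series.

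**Working it through.** The plan gives no power or expected rate for the antibody endpoint, so there is no figure to reproduce. The check has two steps.

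**Step 1. The rule against the series.** Inputs, all from Section 10.n.iv: dilutions 1:25, 1:50, 1:100, 1:200; titre = highest positive dilution; response = at least 4-fold. Reciprocal titre needed = 4 × baseline; largest observable rise = 200 / baseline.

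| Baseline | Titre needed | Run? | Largest observable rise |
|---|---|---|---|
| negative at 1:25 | not defined | – | not defined |
| 1:25 | 4 × 25 = 1:100 | yes | 200/25 = 8-fold |
| 1:50 | 4 × 50 = 1:200 | yes | 200/50 = 4-fold |
| 1:100 | 4 × 100 = 1:400 | no | 200/100 = 2-fold |
| 1:200 | 4 × 200 = 1:800 | no | 200/200 = 1-fold |

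Two of the four measurable baselines cannot meet the definition. The 1:50 row is sound: a true rise of 4-fold or more reads 1:200 and is scored correctly.

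**Step 2. Size of the objective 3 bias, IgG on IgG.** Neither input is in the documents, so both are assumptions shown over a range:

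- p = true 4-fold response rate, the same with or without pre-existing IgG (true odds ratio 1.0);
- s = share of seropositive patients whose baseline is 1:100 or above.

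Observed rate in seropositive patients: o = p × (1 − s). Spurious odds ratio: [o/(1 − o)] / [p/(1 − p)]. With p = 0.30 the reference odds are 0.30/0.70 = 0.429.

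| s | o | o/(1 − o) | Odds ratio |
|---|---|---|---|
| 0% | 0.300 | 0.429 | 1.0 |
| 10% | 0.270 | 0.370 | 0.86 |
| 25% | 0.225 | 0.290 | 0.68 |
| 50% | 0.150 | 0.176 | 0.41 |
| 75% | 0.075 | 0.081 | 0.19 |

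Over p from 10% to 50% and s from 10% to 75%, the odds ratio runs from 0.89 (p = 10%, s = 10%) to 0.14 (p = 50%, s = 75%). With s = 0 there is no bias at any p.

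The calculation also takes the seronegative group to respond at rate p, which presumes that a coding for sera negative at 1:25 has been settled. The plan does not settle it.

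**The case against.** The strongest reply is that little depends on this assay. Section 10.n makes ELISPOT the primary immune method and lists ELISA among methods that may be added. The ELISPOT response definition has no stated ceiling. Both affected objectives are exploratory, immune bloods are drawn only at the lead site, the dilution curves would let a reader see saturated sera, and Section 11.w.i promises a detailed analysis plan in which coding could be settled. All of that stands and sets the severity. None of it supplies the missing rule: responder status is still defined by titre.

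Two escape routes in the text do not close the gap. Substituting another assay is allowed, but nothing triggers it for a serum at the ceiling. The cited titre method is invoked for PAP only and cannot be checked here, while the protocol states its own titre definition.

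A reader might infer more than the documents support:

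- *That these patients can never be responders.* This holds for the listed ELISA series; a substituted assay could have a wider range.
- *That the objective 3 test as a whole is biased.* The bias needs IgG on both sides of the model. T-cell versions and the clinical-response half do not use this outcome.
- *That high-baseline patients will occur.* Pre-existing antibody is expected, but no titres are given, and positives at 1:25 or 1:50 are unaffected.
- *That the overall antibody response rate is understated.* The ceiling alone can only lower it, but a generous coding of conversions from negative could raise it, so the net direction is open.

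**Conclusion.** The point holds for the assay as written. Patients with a baseline of 1:100 or 1:200 are scored as non-responders whatever happens to their antibody, and the 4-fold rule has no meaning for a baseline below 1:25. This follows directly from the stated dilutions and definitions.

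The consequences are conditional. If some patients start at 1:100 or above, true responders are lost from objective 1, and an IgG-on-IgG objective 3 model is biased towards a negative association. The odds ratios above illustrate the size of that bias under assumed p and s; they are not estimates for this trial.

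The severity is minor. Both objectives are exploratory, and ELISPOT-based analyses, clinical response and the primary endpoint are unaffected.

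**What to change.** In Section 10.n.iv, or in the analysis plan still to be written:

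1. Extend the 2-fold series to at least 1:800 for all baseline and post-treatment sera. Stopping at 1:400 would still exclude a baseline of 1:200; 1:800 makes a 4-fold rise visible from all four present baselines.
2. Titrate further any serum still positive at the last dilution. Otherwise sera that now read 1:200 but are truly higher meet the same ceiling again.
3. Fix in advance one value for sera negative at 1:25. One example is 1:12.5, so that a response needs 4 × 12.5 = 1:50 or more. Other conventions would serve if stated beforehand.

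If the series is not extended, report patients with a baseline of 1:100 or above separately, as not assessable for a 4-fold rise rather than as non-responders, and do not interpret an IgG-on-IgG objective 3 model. Simply dropping them from that model is not a repair: it removes the patients with the strongest pre-existing antibody and so changes the question.

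The cost is a few more wells per serum sample. Section 10.n already has sera stored in aliquots at -80°C and allows batched assays, so no new visit or blood draw is needed.
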